No surgical details will deviate from the current standards for operative repair. All wounds will be closed in the fashion deemed appropriate by the operating surgeon. In essence, the only deviation from the expected surgical repair of these injuries will be post-operative monitoring after nerve repair.

Follow Up: Postoperatively, we plan to follow each patient for a total duration of 12 months after repair, anticipating follow up at 1 week, 1 month, 3 months, 6 months, and 12 months post injury. The data to be collected at each visit are shown in **Table 1**.

DTI Acquisitions

Both arms will be scanned in each subject, with data from the uninjured arm serving as an internal control in each patient. Participants will be imaged in the prone position with the arm being imaged extended over the head. Upon completion of the MRI protocol in the 1st arm, participants will be repositioned with the other arm above the head; and the same MRI protocol will be performed in the 2nd arm. To minimize discomfort, the total protocol duration (DTI scans plus additional calibration scans, scout images, T₁-weighted anatomical, and T₂-weighted anatomical protocols) will be less than 30 minutes for each arm.

Human MRI studies will be performed on our 3.0-Tesla Philips Achieva whole-body MR scanner (Philips Healthcare, Best, The Netherlands). A two-channel body coil will be used for excitation, while a multi-element extremity coil will be used for signal reception. We currently have an array of multi-element coils that allow us to perform studies of both distal nerves of the arm. The details of the DTI protocol will be informed from the animal studies and will be optimized during the initial phase (6 months) of this study in healthy subjects. As a starting point, we will rely on previous DTI optimization studies in human median nerve ⁴⁴, which employed a multi-slice diffusion-weighted spin-echo sequence with the following parameters: number of diffusion directions = 15, $b = 1000 \text{ s/mm}^2$, TR/TE = 8000/52 ms, in-plane resolution = 1.0 x 1.0 mm², field-of-view = 80 x 80 mm², number of slices = 25, slice thickness = 4 mm, numbers of signal averages = 4, SENSE acceleration factor = 2, and SPAIR fat suppression. Using this protocol, DTI data can be acquired in approximately 10 minutes, leaving adequate time to complete the entire protocol for each arm within 30 minutes.

Table 1. Demographics and Outcome Variables and follow up for nerve injury patients.

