The eigenvalues/eigenvectors estimated from **D** will also be used to perform fiber tractography, which will be performed using the ExploreDTI toolbox⁷⁰. Seed regions-of-interest (ROIs) of each nerve will be drawn

in the most proximal slice to seed each fiber tract. FA threshold values and the angulation tolerances determine the limits for the automatic tracking of fibers. Previous work⁴³ has determined optimal reconstruction parameters for fiber tractography of healthy nerves (FA threshold = 0.2 and maximum angulation tolerance = 10). We will use these parameters as a starting point, noting that adjustments may need to be made in regenerating nerve. Tractography results will be quantified by estimating the mean length of fiber tracts as well as the relative number of fiber tracts that successfully reach ROIs defined in the most distal slice. During regeneration, we expect mean fiber lengths and relative tract numbers to increase.

Statistics

Statistical analyses will be performed using STATA/IC 13.1 (StataCorp, College Station, TX). In controls, tests will be performed to evaluate i) the relationship between DTI metrics and confounding variables (age, sex, and BMI), ii) the variability of DTI metrics between nerves and along nerve segments and iii) the repeatability of DTI metrics across scans and raters. In patients, tests will be performed to i) evaluate the ability of DTI to predict failed nerve recoveries at each time point (using evaluations at 12 months as the ground truth) and ii) evaluate correlations between the DTI parameters and EMG/NCS results.

We will first examine the potential confounding influence of BMI, age, and sex on each DTI parameter via multiple linear regression in controls. A Shapiro-Wilk test on the regression residuals will be used to test for normality. For the sake of this proposal, we assume normality and that parametric statistical tests are appropriate. We will employ corresponding non-parametric tests if normality is not observed. The effects of BMI, age, and sex on DTI parameters will be quantified via Pearson partial correlation coefficients. To test for variations across nerve and along nerve segments in control subjects, an ANOVA will be performed. If significant variation is observed, post hoc pair-wise comparisons will be performed using a Bonferroni multiple comparison test.

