To understand the ability of DTI parameters to provide estimates of nerve regeneration, it is important to first understand the reliability of the acquisition (interscan) and assessment (interrater) methodology. To estimate the interscan reliability, intraclass correlation coefficients (ICC) will be calculated for each DTI metric in the control scan-rescan data. To test for changes in DTI parameters across time, paired t-tests will also be performed between each timepoint. Finally, the interscan variabilities of DTI parameters will be estimated via the repeatability coefficient (RC), which is defined as 1.96 times the SD of the mean difference between scans. Analogous analyses will be performed for the inter-rater data, where nerve ROIs will be independently defined in 12 control subjects by two trained raters.

Patients will be grouped into “failed” or “successful” cohorts based upon our evaluations at 12 months. All tests below will be performed in three nerve segments of the injured nerve: i) proximal to the injury, ii) at the injury site, and iii) distal to the injury. The percent difference in DTI parameters between injured and non-injured arms will be used in all analyses to control for confounding factors (e.g., age). To evaluate the ability of DTI to predict failed nerve recoveries at each time point, we will perform two sets of test. First, significant difference between “failed” or “successful” groups will be tested (at each time point and nerve segment) via a Bonferroni multiple comparison test. Second, and ROC analysis will be performed to evaluate the diagnostic potential of each normalized DTI parameter at each time point and nerve segment. Finally, to evaluate relationships between DTI parameters and NCS/EMG data (e.g., CMAP), pairwise Pearson correlations and Bonferroni corrected significance values will be calculated.

Potential Pitfalls/Solutions

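### Human tract length and the distal-slice count are tied to the ends of the imaging slab rather than to the repair, so, if tracts stop near the repair, both depend on slab position as well as on regrowth.

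*Combined protocol and SAP*

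**What the plan says.** - **DTI Analysis.** Seed regions are drawn "in the most proximal slice to seed each fiber tract". Results are the "mean length of fiber tracts as well as the relative number of fiber tracts that successfully reach ROIs defined in the most distal slice". The starting FA threshold is 0.2, with adjustment allowed for regenerating nerve.
- **DTI Acquisitions.** The starting protocol has "number of slices = 25, slice thickness = 4 mm". Each session includes "DTI scans plus additional calibration scans, scout images" and anatomical images. Details will be "optimized during the initial phase (6 months) of this study in healthy subjects". Both arms are scanned. The section does not say where the slab sits relative to the repair, or that the position is kept across patients, visits or arms.
- **Patient Population.** Injuries from the mid-forearm distally are eligible. Table 1 records the distance from injury to fingertip at study entry.
- **Statistics.** "All tests below will be performed in three nerve segments of the injured nerve": proximal to, at and distal to the injury. "The percent difference in DTI parameters between injured and non-injured arms will be used in all analyses". Groups are compared at each time point and segment, and "ROC analysis will be performed to evaluate the diagnostic potential of each normalized DTI parameter at each time point and nerve segment". Tract length and tract count are not named there, and no segment version of either is defined.
- **Aim 2** asks whether fiber tracking predicts recovery.

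**The concern.** A tract seeded at the top of the slab that stops at the repair has a length equal to the distance from the top slice to the repair. That distance is set by where the slab was placed. Two patients with the same regrowth can therefore score differently, and two with different regrowth can score the same.

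The safeguards in the plan do not deal with this. An intact nerve can span the slab wherever it sits, so the percent difference from the uninjured arm leaves the offset in. The three injury-based segments suit voxel-wise FA, MD, RD and AD, but a whole-slab tract measure does not belong to any one of them. Optimization in healthy subjects has no repair to refer to. By contrast, the rat tract count that separated transected from sham nerves (Preliminary Findings, DTI of Completely Transected Nerves) was anchored 3 mm either side of the injury.

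At stake is the measure that Aim 2 names. Coverage missed at the scan cannot be recovered later.

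**Working it through.** **The plan's own figure first.** Sample size assumes an FA difference of 10% of 0.5 = 0.05 and SD 0.04, so d = 0.05/0.04 = 1.25. A two-sided pooled t-test at 0.05 with 14 v 10 patients has power 0.82, and 24 is the smallest total that reaches 0.80 at a 40/60 split. The figure reproduces. It concerns FA only and does not depend on tract measures.

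**Geometry.** Slab length L = 25 × 4 = 100 mm (starting protocol, assuming no slice gap). Let d here be the distance from top slice to repair and r the regrowth beyond the repair. If uninjured tracts span the slab, the whole-slab percent difference is (min(d + r, L) − L)/L.

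| Repair at d (mm) | Score, r = 0 | Score, r = 40 mm | Reaches distal slice at r = 40? | Regrowth needed, L − d (mm) |
|---|---|---|---|---|
| 30 | −70% | −30% | no | 70 |
| 50 | −50% | −10% | no | 50 |
| 70 | −30% | 0% | yes | 30 |

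Forty millimetres of regrowth at d = 30 gives the same score as none at d = 70.

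**Size for tract length.** The documents give no spread for placement or regrowth, so these inputs are assumptions: mean regrowth 30 mm (successful) v 10 mm (failed), floored at 0; regrowth SD 10 or 20 mm; repair centred at 50 mm with placement SD s; one tract length per patient; every uninjured tract exactly L. Without truncation, AUC = Φ(20/√(2(SD² + s²))). For SD 10 and s = 20 this is Φ(20/√1000) = 0.74. Simulation with truncation at the slab end, 400,000 per group:

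| Measure | Regrowth SD (mm) | s = 0 | s = 5 | s = 10 | s = 20 |
|---|---|---|---|---|---|
| Whole-slab percent difference | 10 | 0.92 | 0.90 | 0.84 | 0.73 |
| Percent difference, distal segment only | 10 | 0.92 | 0.92 | 0.90 | 0.86 |
| mm beyond the repair | 10 | 0.92 | 0.92 | 0.92 | 0.90 |
| Whole-slab percent difference | 20 | 0.76 | 0.75 | 0.73 | 0.67 |
| mm beyond the repair | 20 | 0.76 | 0.76 | 0.76 | 0.74 |

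The Hanley-McNeil standard error with 14 v 10 patients runs from 0.06 (AUC 0.92) to 0.11 (AUC 0.67). For the whole-slab measure with regrowth SD 10 mm, unadjusted t-test power with effect size 20/√(100 + s²) is 0.996, 0.985, 0.90 and 0.54. The plan's Bonferroni correction would lower these.

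**The distal-slice count.** In the same model with SD 10 mm and perfect placement, a repair at 50 mm needs 50 mm of regrowth. About 2% v 0% of patients reach it, so AUC = 0.5 + (0.023 − 0.000)/2 = 0.51. At s = 20 mm the figures are about 19% v 4%, AUC 0.57. A count at a fixed 20 mm beyond the repair, with perfect placement, gives 84% v 16%, AUC 0.84.

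**How tract measures enter the tests.** Three readings are open. As a whole-slab percent difference, placement enters fully. Computed for the distal segment, it enters more weakly, through the uninjured length below the repair level. If the DTI parameters in Statistics exclude tractography, as Aim 1 Task 1 suggests by listing it apart from the DTI metrics, the fiber-tracking question in Aim 2 has no specified test.

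**The case against.** The strongest objections, and what stands of each:

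- **Tracts may not stop at the repair.** The starting FA threshold of 0.2 is well below the post-injury FA of 0.5 assumed under Sample size, so some tracts may pass through, and those would carry little placement dependence. This stands as a condition on the point. One human pilot patient (Fig 11) did show shorter tracts in the injured nerve, which supports the mechanism but cannot show that lengths compare across repair levels.
- **Slabs may already be well placed.** The three segments require coverage on both sides of the injury, scout and anatomical images are taken, and the protocol is provisional. If operators place slabs consistently on the repair, there is no loss. But the rule is not written, and coverage on both sides alone does not bound the effect tightly: with regrowth SD 10 mm and the repair anywhere at least 20 mm from both ends, whole-slab AUC is 0.745; at least 40 mm, 0.888.
- **The size depends on the assumptions.** This is correct. With regrowth SD 20 mm, a 10 mm placement SD costs about 0.03 of AUC, well inside the standard error. Even the fall from 0.92 to 0.84 is about one standard error. No general threshold at which the loss starts to matter can be given.
- **The uninjured arm is idealised.** The hind-limb section reports short tracts from single-slice seeding even at low FA thresholds, so uninjured tracts may not span the slab. The normalisation also guards against confounders such as age, which is a reason to keep a percent difference alongside a length in millimetres.

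A reader might infer that placement noise is what spoils the distal-slice count. The model does not show that: the count is weakest with perfect placement, because the target lies so far beyond the repair. Nor would visit-to-visit shifts in the slab pass for regrowth under the specified patient tests, which compare groups at each time point rather than tract length across visits.

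**Conclusion.** The point holds conditionally. The tract rule as written gives different scores for identical regrowth when the slab sits differently, provided tracts stop at or near the repair. It affects the failed-versus-successful and ROC analyses only if tract measures enter them; if they do not, the gap is that Aim 2's fiber-tracking question has no test. Either way the text needs a change.

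The size for tract length is unknown. It ranges from nothing, with consistent placement, to an AUC fall of about 0.19 under the less favourable assumptions (regrowth SD 10 mm, placement SD 20 mm). The distal-slice count has its own fault, a far target that differs between patients, and is near chance in the same model.

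A reader might infer that the patient comparison as a whole is compromised or that the trial is too small. The documents do not support that: the 24 patients are sized on FA, and the FA, MD, RD and AD analyses have injury-based segments. This is a change that should be made to the tractography measures, held with medium confidence.

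**What to change.** 1. **DTI Analysis, length:** define tract length as millimetres beyond the repair slice. Report it alongside a percent difference from the uninjured arm at matched levels, not only as that percent difference.
2. **DTI Analysis, count:** replace or supplement the distal-slice count with the share of proximally seeded tracts that cross the repair and reach a fixed distance beyond it, within coverage common to all patients.
3. **DTI Acquisitions:** place the slab at a set offset from the repair, using the scout and anatomical images already taken, and match it across visits and arms.
4. **Statistics:** state that these tract measures enter the failed-versus-successful and ROC tests, and in what form.

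The scanner, sequence and software stay the same. The cost is a short positioning step, a little analyst time and protocol wording. Coverage beyond very distal repairs is limited, so the common distance must be stated and may be short. A short distance caps the measure: in the model with regrowth SD 10 mm and perfect placement, length as a share of 20 mm gives AUC 0.88 instead of 0.92.

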[name]/PhD is an Assistant Professor of Plastic, Orthopedic Surgery, and Biomedical Engineering. His role in this project is to provide clinical expertise and applicability. He is the primary hand surgeon for the Plastic Surgery Service at Vanderbilt, Chief of Plastic Surgery at the Nashville Veterans Hospital, and maintains a funded basic science laboratory devoted to nerve repair. He has eight peer-reviewed publications focusing on nerve repair using animal models of peripheral nerve injury (see biosketch).

The Vanderbilt Medical Group performed over 372 pure sensory nerve repairs in 2010 and an additional 50 repairs involving mixed nerve loss in the upper extremity. [name] would have direct access to at least ½ of these repairs. Given this, for the each cohort, sensory, motor, mixed, we anticipate a study recruitment duration less than 24 months to allow 12 month follow up. Patient recruitment will continue until 24 are included and follow up will be for minimum 12 months. For the control cohort requiring we anticipate total study duration less than 24 months and follow-up for at least 12 months. Patient recruitment will continue until 24 are included (approximately 24 months) and follow up will be for 12 months. Assuming a 40% failure rate, this would give us 14 responders and 10 non-responders. Given that we expect to be able to recruit 10-20 patients/year for each group: (sensory, motor, mixed), we expect to reach this target within the 1st 2 yr-year period of this award, allowing for a 6-12 month follow up for all patients. Given our # of patients seen- all patients should be recruited within the first 2 years of the study.

[name] (Collaborator)

[name], PhD is an Assistant Professor of Radiology and Radiological Sciences, Biomedical Engineering, Vanderbilt University. His role in this project is to provide technical expertise for the human DTI studies. He is currently funded to develop, translate, and validate quantitative MRI measures of peripheral nerve pathology and function in humans. As part of this funding, his lab has developed DTI protocols for the nerves of the wrist, which will serve as the basis for the proposed human imaging studies. He has published multiple peer-reviewed articles directly related to the development of quantitative MRI techniques for applications in the human neuromuscular system; and has extensive experience in developing and translating quantitative MRI techniques into clinical populations (see biosketch).

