Exclusion criteria: Patients will be excluded from enrollment if their injuries exhibit gross contamination, in circumstances where soft tissue coverage is inadequate, or when staged repair is planned. We will also exclude patients that are diabetic, have been diagnosed with a neuromuscular disease, or are undergoing chemotherapy, radiation therapy, or other treatments known to affect the growth of the neural and vascular system. We will exclude all patients currently enrolled in another investigational study or those who are unlikely to complete the normal regime of occupational therapy. For safety reasons, all pregnant women or women who are breast-feeding will also be excluded from this study along with subject with any ferromagnetic objects that cannot be removed (cardiac pacemakers, aneurysm clip, etc.), and/or a history of claustrophobia. All subjects will undergo a standardized MRI metal screening prior to each MRI scan, and signed consent will be obtained prior to all examinations.

Sample size: Previous optimization DTI studies in human median nerves reported mean (\pm SD) FA values of 0.7 ± 0.04 ⁴². We do not have human longitudinal data from which we can estimate an effect size; however, Takagi et al.²² performed ex vivo DTI in a rat injury model longitudinally and reported mean FA values of 0.5 following trauma (FA values are preserved across fixed and in vivo tissue⁶⁴). We, therefore, assume a similar mean FA value after surgery (0.5) with a SD taken from the aforementioned human optimization study (0.04) for our power analysis below. A conservative goal is to detect a 10% increase in FA from this decreased value to stratify successful from unsuccessful surgical interventions. If we test for

differences between these cohorts via a two-tailed pooled Student's t-test ($p = 0.05$), 24 patients would yield a study power of 0.8. Thus, assuming a failure rate of 40%, we will scan 24 patients, approximately 14 of which should have successful surgeries and 10 of which should have unsuccessful surgeries.

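### As worded, the repeatability coefficient is built on a standard error; followed literally, it would understate scan and rater variability by a factor of √n

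*Combined protocol and SAP*

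**What the plan says.** The reliability paragraph of the Statistics section (combined protocol and SAP) sets out three analyses of repeat scans in controls. First, "intraclass correlation coefficients (ICC) will be calculated for each DTI metric in the control scan-rescan data". Second, paired t-tests look for a shift between scan occasions. Third, interscan variability is to be estimated by the "repeatability coefficient (RC), which is defined as 1.96 times the SD of the mean difference between scans".

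The paragraph then extends the set to raters: "Analogous analyses will be performed for the inter-rater data", where "nerve ROIs will be independently defined in 12 control subjects by two trained raters".

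No other section gives a different formula for the coefficient, or says that the SD of the individual differences is meant. The number of controls to be scanned twice is not stated.

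**The concern.** A repeatability coefficient answers a question about one subject: how far apart can two measurements of the same nerve be when nothing has changed? That calls for the spread of the individual paired differences. The SD of the mean difference answers another question, namely how precisely the average shift between scans is known. It can be made as small as one likes by adding controls, with no gain in the repeatability of the scanner or the raters. The formula therefore does not serve the purpose that its own sentence gives it.

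At stake is the one planned reliability statistic expressed in the units of the metric itself. The ICC is unitless and depends on the spread between subjects, and the paired t-test addresses only an average shift. Neither would expose a coefficient that was too small. The study develops a monitoring tool, so readers are likely to look to this figure when judging whether a change in one nerve is more than measurement noise.

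**Working it through.** The plan states no numerical value for the coefficient, so there is no figure to reproduce. The check is of the formula.

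**Inputs**
- Multiplier 1.96 and the definition: Statistics section.
- Rater comparison: n = 12 controls, two raters (Statistics section).
- Scan-rescan comparison: n not stated. I use 24 as an assumption. That number appears in the Previous Experience section for patient recruitment, next to an unclear mention of a control cohort and with no mention of rescans.
- SD of the paired differences, s_d: not given. For illustration I assume 0.02 to 0.06 FA units. The ratio and coverage results below do not depend on it.

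**Step 1: the two formulas.** Let d be the paired difference in one subject, s_d its SD across subjects, and s_w the within-subject SD, so that s_d = √2 × s_w.
- Standard coefficient: RC = 1.96 × s_d = 1.96 × √2 × s_w.
- As worded: 1.96 × SD(mean d) = 1.96 × s_d/√n.

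**Step 2: the ratio.** Standard divided by worded = √n.
- n = 12: √12 = 3.46.
- n = 24 (assumed): √24 = 4.90.

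A simulation with 200,000 replicates gave ratios of 3.46 to 3.47 for n = 12 and 4.90 to 4.92 for n = 24.

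**Step 3: coverage.** With normal differences, no systematic bias and s_d taken as known, the worded limits cover a single new difference with probability 2Φ(1.96/√n) − 1.
- n = 12: 1.96/3.46 = 0.566, giving 0.43.
- n = 24 (assumed): 1.96/4.90 = 0.400, giving 0.31.

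The intended coverage is 0.95.

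**Step 4: illustration in FA units (s_d assumed).**

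| s_d | 1.96 × s_d | As worded, n = 12 | As worded, n = 24 (assumed) |
|---|---|---|---|
| 0.02 | 0.039 | 0.011 | 0.008 |
| 0.04 | 0.078 | 0.023 | 0.016 |
| 0.06 | 0.118 | 0.034 | 0.024 |

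**Step 5: where the coefficient is used.** I traced the other analyses in the Statistics and Sample size paragraphs. Patients are classed as failed or successful from the 12-month evaluations. The group tests and the ROC analysis use the normalised difference between a patient's two arms. The link to NCS/EMG uses Pearson correlations. The sample size uses a two-sample t-test. None of these takes the coefficient as an input.

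**The case against.** The strongest reply is that this is a slip of wording. The sentence names a standard statistic, uses its usual multiplier and says that it is to estimate variability between scans, all of which point to the ordinary definition. The phrase could loosely mean the SD reported beside the mean difference, or the SD of per-subject differences in ROI-averaged values, since the metrics are computed voxel by voxel and raters draw ROIs. An analyst who knows the method may well compute it correctly. This stands as a limit on certainty: the error occurs only if the wording is followed. It does not remove the point, because the text states neither alternative and the definition is explicit.

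Two stronger readings are tempting, and the documents do not support them.

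- A reader might infer that scan noise would be taken for regeneration or failure in patients. No rule in the plan compares a patient's change with the coefficient, and no patient analysis uses it.
- A reader might infer that the FA change behind the sample size lies inside measurement noise. The Sample size paragraph says "A conservative goal is to detect a 10% increase in FA from this decreased value", which is 10% of 0.5 = 0.05. But that is a contrast between two cohorts, whereas the coefficient is a limit for one subject's repeat difference. The patient analyses also use a percent difference between arms, not raw FA. And the comparison hangs on an SD that the documents do not give: at s_w = 0.020 the standard coefficient is 1.96 × 1.414 × 0.020 = 0.055, above 0.05; at s_w = 0.018 it is 0.0499, just below.

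**Conclusion.** The point holds, conditional on the literal reading. As written, the formula yields a standard error and cannot measure interscan or inter-rater variability. For raters, where n = 12 is stated, the coefficient would be 3.46 times too small and its nominal 95% limits would cover about 43% of single repeat differences. For repeat scans the size cannot be fixed, because n is not stated; 4.90-fold and about 31% apply only if n is 24. The ratio needs no assumption about the noise level. The coverage figures assume normal differences and no systematic bias.

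The consequence is limited to the reported repeatability of the DTI metrics and what readers make of it. The test of whether DTI predicts failed recovery is unaffected. It is still worth correcting before analysis, because the error runs in the flattering direction and nothing else planned would reveal it.

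**What to change.** In the reliability paragraph of the Statistics section, define RC = 1.96 × SD of the individual between-scan differences, equivalently 1.96 × √2 × within-subject SD, and say that the rater analysis uses the between-rater differences in the same way. Report the mean difference with its confidence interval separately, as the estimate of bias. State how many controls will be scanned twice.

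This takes a sentence or two and needs no new data or change of design. The cost is that the reported coefficient will be larger and less favourable than the literal formula would give. If the standard definition was intended all along, the edit only makes that explicit.
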